- After vaccination, if the subjects or the subject's parents/adoptive parents observe any large injection site reaction (~~defined as a swelling with a diameter of >50 mm for subjects <6 years of age and >100 mm for subjects ≥6 years of age~~ **for subjects <6 years of age defined as a swelling with a diameter of >50 mm and for subjects ≥6 years of age swelling with a diameter of >100 mm**, noticeable diffuse swelling or noticeable increase in limb circumference) during the 4-day follow-up (Day 1-4) period, they will be asked to contact study personnel and to visit the investigator's office for evaluation as soon as possible. The investigator *or delegate* will record detailed information describing the AE on a specific large injection site reaction screen in the eCRF.

Throughout the document for the procedures for the investigator, “**or delegate**” was added as appropriately.

Section 5.6.13: Return of diary card and diary card transcription

- Any unreturned diary cards will be sought from the subject/subject's parent(s)/adoptive parent(s) through telephone call(s) or any other convenient procedure. The investigator *or delegate* will transcribe the collected information into the eCRF in English.

Section 5.6.14: Recording of AEs, SAEs and pregnancies

- Refer to Section 8.3 for procedures for the investigator *or delegate* to record AEs, SAEs, pregnancies. Refer to Section 8.4 for guidelines and how to report SAE and pregnancy reports to GSK Biologicals.
- The *subject*/subjects' parent(s)/adoptive parent(s) will be instructed to contact the investigator immediately should they/the subjects manifest any signs or symptoms they perceive as serious.

Section 5.7.3: Laboratory assays

All serology will be determined in GSK Biologicals' laboratories or in a laboratory designated by GSK using standardized and validated procedures with adequate controls.

Refer to Table 8 for the assays used in antibody determination.

Table 8 Humoral Immunity (Antibody determination)

System	Component	Method	Kit / Manufacturer	Unit	Cut-off†	Laboratory*
Serum	Corynebacterium diphtheriae .Diphtheria Toxoid Ab.IgG	ELI	NA	IU/ml	0.057 †	GSK Biologicals or designated laboratory
Serum	Corynebacterium diphtheriae .Diphtheria Toxoid Ab	NEU assay on Vero cells**	NA	IU/ml	0.004	GSK Biologicals or designated laboratory
Serum	Clostridium tetani .Tetanus Toxoid Ab.IgG	ELI	NA	IU/ml	0.043 †	GSK Biologicals or designated laboratory
Serum	Bordetella pertussis .Pertactin Ab.IgG	ELI	NA	IU/ml EU/ml [§]	2.6935	GSK Biologicals or designated laboratory
Serum	Bordetella pertussis .Filamentous Hemagglutinin Ab.IgG	ELI	NA	IU/ml EU/ml [§]	2.0465	GSK Biologicals or designated laboratory
Serum	Bordetella pertussis .Pertussis Toxin Ab.IgG	ELI	NA	IU/ml EU/ml [§]	2.1875	GSK Biologicals or designated laboratory

ELI: ELISA

NEU: Neutralisation assay**NA: Not Applicable**

IU/ml: International Units per millilitre

The assay cut-off for diphtheria, tetanus and pertussis may be subject to change.

EU/ml: ELISA units per millilitre

-[§]The unit for the pertussis assays may be subject to change.

†Assays for diphtheria, tetanus and pertussis were re-developed and re-validated as per most recent CBER recommendations (Guidance for Industry "Bioanalytical Method Validation" from September 2013). The new assay cut-off's that apply are listed in the table.

*GSK Biologicals laboratory refers to the Clinical Laboratory Sciences (CLS) in Rixensart, Belgium and Wavre, Belgium.

**Test on Vero-cells will be performed on pre- and post-vaccination samples with concentrations <0.1 IU/ml by ELISA.

Section 5.7.5: Immunological correlates of protection

The following cut-offs are accepted as immunological correlates of protection:

- Specific antibodies against diphtheria toxoid (*anti-diphtheria*) and tetanus toxoid (*anti-tetanus*) will be measured by *enzyme-linked immunosorbent assay* (ELISA). The *newly validated* assay cut-off for anti-diphtheria is currently set at ~~0.1 IU/ml (ELISA)~~ **0.057 IU/ml** and for anti-tetanus at **0.043 IU/ml**. For both serology a **threshold of 0.1 IU/ml** which provides a conservative estimate of the percentage of subjects deemed to be protected [Camargo, 1984; Melville-Smith, 1983].
- The cut-off of the Vero-cell *neutralisation* assay (performed for pre- and post-vaccination serum samples when ELISA *anti-diphtheria* antibody concentrations are <0.1 IU/ml) is 0.004 IU/ml. Antibody concentrations ≥0.01 IU/ml are considered as protective [Camargo, 1984]. The ELISA test will define the seroprotection status for the primary endpoint.

- No *serological* correlate of protection is defined for the immune response to pertussis antigens. Antibodies against the pertussis components PT, FHA and PRN will be measured by ELISA technique. ~~The current cut-off for all three pertussis antibody assay is 5 ELISA Units per ml (EL.U/ml).~~ **The newly validated assay cut-off for anti-PT is 2.693 IU/ml, for anti-FHA is 2.046 IU/ml and for anti-PRN is 2.187 IU/ml.** Subjects with antibody concentration below this cut-off will be considered seronegative. ~~[Granstrom, 1987; Karpinsky, 1987].~~

Non-responders are defined as:

- Antibody concentrations <0.01 IU/ml post-booster for diphtheria antigen by Vero-cell *neutralisation* assay and,
- Antibody concentrations <0.1 IU/ml post-booster for tetanus antigen by ELISA assay

Section 6.3: Dosage and administration of study vaccine

The vaccine will be administered as an IM injection into the deltoid muscle of the non-dominant arm, i.e. in the left arm if the subject is right-handed or in the right arm if the subject is left-handed. ***In case it is not possible for a valid reason to inject in the non-dominant arm, an injection in the dominant arm may be performed.*** *Boostrix* should in no circumstances be administered intravascularly.

Section 6.5: Contraindications to vaccination

Since this is a single dose study, contraindications to vaccination are included in the exclusion criteria. Refer to Section 4.3.

~~The following events constitute contraindications to further administration of *Boostrix*. during the study, the subject must not receive additional doses of vaccine but may continue other study procedures at the discretion of the investigator (see Section 8.5).~~

The following events constitute contraindications to administration of *Boostrix* at that point in time; if any of these events occur at the time scheduled for vaccination, the subject may be vaccinated at a later date, within the time window specified in the protocol (see Section 6.7.1), or the subject may be withdrawn at the discretion of the investigator (see Section 6.7.2).

Section 6.6: Warnings and precautions

~~Refer to the package insert of *Boostrix*.~~ ***As with all injectable vaccines, appropriate medical treatment should always be readily available in case of anaphylactic reactions following the administration of the vaccine. For this reason, the vaccinee should remain under medical supervision for 30 minutes after vaccination.***

Boostrix vaccination should be administered with caution to subjects with thrombocytopenia or a bleeding disorder since bleeding may occur following an intramuscular (IM) administration to these subjects.

Boostrix vaccination should under no circumstances be administered intravenously.

Section 6.7.2: Concomitant medications/products/vaccines that may lead to the elimination of a subject from per protocol analyses

- In case an emergency mass vaccination for an unforeseen public health threat (e.g.: a pandemic) is organised by the public health authorities, outside the routine immunisation program, the time period described above can be reduced if necessary for that vaccine provided it is licensed and used according to its Summary of Product Characteristics (SmPC) ~~or PI~~ and according to the local governmental recommendations and provided a written approval of the Sponsor is obtained.

Section 8.1.3.1: Solicited local (injection-site) adverse events

Note: If the subjects or the subject's parent(s)/adoptive parent(s) observe any large injection site reaction (~~defined as a swelling with a diameter of > 50 mm for subjects <6 years of age and >100 mm for subjects ≥6 years of age, for subjects <6 years of age defined as a swelling with a diameter of > 50 mm and for subjects ≥6 years of age swelling with a diameter of >100 mm~~, noticeable diffuse swelling or noticeable increase in limb circumference) during the 4-day (Day 1–4) follow-up period after vaccination, they will be asked to contact the study personnel and to visit the investigator's office for evaluation as soon as possible. The investigator *or delegate* will record detailed information describing the AE on a specific large injection site reaction sheet in the eCRF.

Section 8.2.1: Pregnancy

Furthermore, any SAE occurring as a result of a post-study pregnancy and considered by the investigator to be reasonably related to the study vaccine will be reported to GSK Biologicals as described in Section 8.4.3. While the investigator *or delegate* is not obligated to actively seek this information from former study participants, he/she may learn of a pregnancy through spontaneous reporting.

Section 8.3.1: Time period for detecting and recording adverse events, serious adverse events and pregnancies

All AEs starting within ~~three~~ **30** days following administration of the dose of study vaccine (~~Day 1–4~~ **Day 1–31**) must be recorded onto the appropriate section of the eCRF, irrespective of intensity or whether or not they are considered vaccination-related.

Section 8.3.2: Post-Study adverse events and serious adverse events

A post-study AE/SAE is defined as any event that occurs outside of the AE/SAE reporting period defined in Table 14. Investigator(s) *or delegate(s) is/are* not obligated to actively seek AEs or SAEs in former study participants. However, if the investigator learns of any SAE at any time after a subject has been discharged from the study, and he/she considers the event reasonably related to the investigational vaccine, the investigator will promptly notify the Study Contact for Reporting SAEs.

Section 8.3.3.1: Active questioning to detect adverse events and serious adverse events

When an AE/SAE occurs, it is the responsibility of the investigator to review all documentation (e.g. hospital progress notes, laboratory and diagnostics reports) relative to the event. The investigator *or delegate* will then record all relevant information regarding an AE/SAE in the eCRF. The investigator *or delegate* is not allowed to send photocopies of the subject's medical records to GSK Biologicals instead of appropriately completing the eCRF. However, there may be instances when copies of medical records for certain cases are requested by GSK Biologicals. In this instance, all subject identifiers will be blinded on the copies of the medical records prior to submission to GSK Biologicals.

Section 8.3.3.2.1: Assessment of intensity

The maximum intensity of fever will be scored at GSK Biologicals as follows:

0	=	<37.5°C
1	=	≥37.5°C to ≤38.0°C
2	=	>38.0°C to ≤39.0°C
3	=	>39.0°C
0	=	<38 °C
1	=	≥38.0 °C to ≤39.0 °C
2	=	>39.0 °C to ≤40.0 °C
3	=	>40.0 °C

Section 8.3.3.2.2: Assessment of causality

Alternative plausible causes, such as natural history of the underlying diseases, concomitant therapy, other risk factors, and the temporal relationship of the event to the study vaccine will be considered and investigated. The investigator will also consult the IB and/or SmPC and/or PI for marketed products to determine his/her assessment.

Section 8.4.3: Completion and transmission of SAE reports to GSK Biologicals

Once an investigator becomes aware that a SAE has occurred in a study subject, the investigator (or designate) must complete the information in the electronic Expedited Adverse Events Report WITHIN 24 HOURS. The report will always be completed as thoroughly as possible with all available details of the event. Even if the investigator *or delegate* does not have all information regarding a SAE, the report should still be completed within 24 hours. Once additional relevant information is received, the report should be updated WITHIN 24 HOURS.

Section 9.2.1: Subject withdrawal from the study

Information relative to the withdrawal will be documented in the eCRF. The investigator *or delegate* will document whether the decision to withdraw a subject from the study was made by the subject himself/herself, by the subject's parent(s)/adoptive parent(s), or by the investigator, as well as which of the following possible reasons was responsible for withdrawal:

*In case a subject is withdrawn from the study because he/she/the subject's parent(s)/adoptive parent(s) has withdrawn consent, the investigator *or delegate* will document the reason for withdrawal of consent, if specified by the subject/subject's parent(s)/adoptive parent(s), in the eCRF.

Section 10.5: Derived and transformation data

- A seroprotected subject is a subject whose antibody concentration is greater than or equal to the level defining clinical protection. The following seroprotection thresholds are applicable:
 - Anti-Diphtheria antibody concentrations \geq ~~assay cut-off~~ **0.1 IU/ml**.
 - Anti-Tetanus antibody concentrations \geq ~~assay cut-off~~ **0.1 IU/ml**.
- Booster response to *Diphtheria* and *Tetanus* antigens is defined as:
 - for initially seronegative subjects *with* pre-vaccination **antibody** concentration **<0.1 IU/ml (i.e. below the seroprotection cut-off)** (~~pre-vaccination concentration below assay cut-off~~), antibody concentrations at least ~~four times the assay cut-off~~ **≥ 0.4 IU/ml**, one month after vaccination, and
 - for initially seropositive subjects *with* pre-vaccination **antibody** concentration **≥ 0.1 IU/ml (i.e. equal or above the seroprotection cut-off)**, an increase in antibody concentrations of at least four times the pre-vaccination concentration, one month after vaccination.
- Booster response to PT, FHA and PRN antigens is defined as:
 - for subjects with pre-vaccination antibody concentration below (i.e. ~~\leq~~) the assay **cut-off**, post-vaccination concentration \geq four times the assay **cut-off**,
 - for subjects with pre-vaccination antibody concentration between the assay **cut-off** and below (i.e. ~~\leq~~) four times the assay **cut-off**, post-vaccination antibody concentration \geq four times the pre-vaccination **antibody** concentration, and
 - for subjects with pre-vaccination antibody concentration \geq four times the assay **cut-off**, post-vaccination antibody concentration \geq two times the pre-vaccination **antibody** concentration.

Section 10.7: Analysis of immunogenicity

- Booster response rate one month post-vaccination will be calculated with exact 95% CIs for *diphtheria, tetanus and* pertussis antigens.

Section 10.8: Analysis of safety

The ~~overall incidence~~ **percentage of subjects** with at least one local symptom (solicited or unsolicited), with at least one general symptom (solicited or unsolicited) and with any symptom (solicited or unsolicited) during the 4-day (Day 1-4) follow-up period after booster vaccination will be tabulated with exact 95% CI after booster vaccination.

Any large injection site reaction (~~defined as a swelling with a diameter of >50 mm for subjects <6 years of age and >100 mm for subjects ≥ 6 years of age~~ **for subjects <6 years**

of age defined as a swelling with a diameter of > 50 mm and for subjects ≥6 years of age swelling with a diameter of >100 mm, noticeable diffuse swelling or noticeable increase in limb circumference) onset during the 4-day (Day 1-4) follow-up period after vaccination will be described in detail.

Section 13: Reference

~~Karpinsky KF, Hayward S and Tryphonas H. Statistical considerations in the quantitation of serum immunoglobulin levels using the enzyme-linked immunosorbent assay (ELISA). *J Immunol Methods*, 1987; 103: 189-94.~~

Appendix A: Clinical Laboratories

Table 26 — Outsourced Laboratories

Laboratory	Address
NEOMED LABS Inc (formerly GSK GVCL Laval)	[name]
Q ² Solutions	[name]

Throughout the document 100.4°F was removed since the scale Fahrenheit is not used for measuring temperature in Russia.

GlaxoSmithKline Biologicals SA	
Vaccines R &D	
Protocol Amendment 3	
eTrack study number and Abbreviated Title	201532 [DTPA (BOOSTRIX)-050]
IND number	BB-IND-8461
EudraCT number	2015-003405-42
Amendment number:	Amendment 3
Amendment date:	31 October 2017
Co-ordinating author:	PPD [REDACTED], Scientific Writer
Rationale/background for changes:	

This protocol amendment was developed in order to accommodate older adults (approximately 58 years old and older) who were born before national recommendations in Russia for infant DTP vaccination. The protocol amendment will also clarify inconsistencies present in the Protocol Amendment 2, between the English version and the Russian version. Following which, adjustments to the text were made in the inclusion criteria to clarify the enrolment of subjects for age group eight years and above.
	

Amended text has been included in ***bold italics*** and deleted text in **strikethrough** in the following sections:

Protocol Amendment 3 Investigator Agreement

To ensure that no clinical samples (including serum samples) are retained onsite or elsewhere without the approval of GSK Biologicals and the express written informed consent of the subject and/or the subject's ~~legally acceptable representative~~ ***parent(s)/adoptive parent(s)***.

Section 4.2: Inclusion criteria for enrolment

Subjects eight years of age and older who can report previous diphtheria, tetanus ~~and~~ ***with or without*** pertussis vaccination – documented or to the best of their/subjects' parent(s)/subjects' adoptive parent(s) knowledge – and did not receive an additional diphtheria, tetanus ***with*** or ***without*** pertussis vaccination within five years prior to enrolment in the study will be enrolled.

Section 5.1: Regulatory and ethical considerations, including the informed consent process

In accordance with the ICH Harmonised Tripartite Guidelines for Good Clinical Practice, those subjects who can only be enrolled in the study with the consent of the subject's ***parent(s)/adoptive parent(s)*** ~~legally acceptable representative~~ (e.g. minors), should be informed about the study to the extent compatible with the subject's understanding and, if

capable, the subject should sign and personally date a written informed assent form (IAF). It is required that the assent be signed by each subject, if capable, in addition to the informed consent that is to be signed by his/her legal representative. It should be assessed whether an assent is required depending of the age of the study population and the local requirements.

Section 5.6.4: Medical history and vaccination history

Review the subject's* childhood diphtheria, tetanus, *with or without* ~~and~~ pertussis, vaccinations to collect information on the vaccine name, route of administration, dose number and date of administration. This information should be recorded in the eCRF.

*For subjects eight years and older, with no documented previous diphtheria, tetanus, *with or without* ~~and~~ pertussis, vaccinations, details are to be recorded to the best of their/subjects' parent(s)/subjects' adoptive parent(s) knowledge.

Section 5.7.3: Laboratory assays (Table 8: footnote)

ELISA's Assays for diphtheria, tetanus and pertussis were re-developed and re-validated as per most recent CBER recommendations (Guidance for Industry "Bioanalytical Method Validation" from September 2013). The new assay cut-offs that apply are listed in the table. ***The neutralisation assay for Diphtheria is still under re-development and the assay cut-off might be subject to change during the course of the study. In this case, it will be documented in the clinical study report.***

Section 5.7.5: Immunological correlates of protection

The cut-off of the Vero-cell neutralisation assay (performed for pre- and post-vaccination serum samples when ELISA anti-diphtheria antibody concentrations are <0.1 IU/ml) is 0.004 IU/ml. Antibody concentrations ≥ 0.01 IU/ml are considered as protective [***WHO, 1994-Camargo, 1984***]. ***Both, the ELISA test (antibody concentrations ≥ 0.1 IU/ml) and Vero-cell test (antibody concentrations ≥ 0.01 IU/ml)*** will define the seroprotection status for the primary endpoint.

Section 10.5: Derived and transformed data

Anti-diphtheria antibody concentrations ≥ 0.1 IU/ml ***for ELISA assay and ≥ 0.01 IU/ml for Vero-cell assay.***

Section 13: References

Efstratiou A. & Maple P.A.C., 1994. Diphtheria. Laboratory diagnosis of Diphtheria. The expanded programme on immunization in the European region of WHO. WHO ICP/EPI 038 (C). World Health Organization, Geneva, Switzerland.

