5.7.5. Immunological correlates of protection

The following cut-offs are accepted as immunological correlates of protection:

- Specific antibodies against diphtheria toxoid (anti-diphtheria) and tetanus toxoid (anti-tetanus) will be measured by enzyme-linked immunosorbent assay (ELISA). The newly validated assay cut-off for anti-diphtheria is currently set at 0.057 IU/ml and for anti-tetanus at 0.043 IU/ml. For both serology a threshold of 0.1 IU/ml provides a conservative estimate of the percentage of subjects deemed to be protected [Camargo, 1984; Melville-Smith, 1983].
- The cut-off of the Vero-cell neutralisation assay (performed for pre- and post-vaccination serum samples when ELISA anti-diphtheria antibody concentrations are <0.1 IU/ml) is 0.004 IU/ml. Antibody concentrations ≥ 0.01 IU/ml are considered as protective [WHO, 1994]. **Both the ELISA test (antibody concentrations ≥ 0.1 IU/ml) and Vero-cell test (antibody concentration ≥ 0.01 IU/ml) will define the seroprotection status for the primary endpoint. (Amended 31 October 2017)**
- No serological correlate of protection is defined for the immune response to pertussis antigens. Antibodies against the pertussis components PT, FHA and PRN will be measured by ELISA technique. The newly validated assay cut-off for anti-PT is 2.693 IU/ml, for anti-FHA is 2.046 IU/ml and for anti-PRN is 2.187 IU/ml. Subjects with antibody concentration below this cut-off will be considered seronegative.

The immunological assay results will be communicated to the investigator as soon as they become available.

The investigator is encouraged to share the immunological assay results for non-responders with the study subjects/subjects' parent(s)/adoptive parent(s).

For the subjects identified as non-responders, it remains the responsibility of the investigator in charge of the subject's clinical management to determine the medical need for re-vaccination and to re-vaccinate the subjects as per local/regional practices.

Non-responders are defined as:

- Antibody concentrations <0.01 IU/ml post-booster for diphtheria antigen by Vero-cell neutralisation assay and,
- Antibody concentrations <0.1 IU/ml post-booster for tetanus antigen by ELISA assay.

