10.3. Determination of sample size

The primary objective of the study is to assess the immunological response to the study vaccine in terms of seroprotection status for diphtheria, tetanus and in terms of seropositivity for the pertussis antigens, one month after vaccination.

According to Russian regulations, for the purpose of product registration, the minimum sample size required is 100 subjects in each age group. Therefore, the total number of evaluable subjects is 400 [100 subjects in each age group, 4-9 years (children), 10–17 years (adolescents), 18-64 years (adults) and ≥65 years (elderly population)]. Assuming a drop-out rate of 10%, to compensate for subject attrition due to early withdrawal, a total of 448 subjects (112 in each age group) will be enrolled in to the study in order to obtain the desired number of evaluable subjects for analysis.

Table 18, Table 19, Table 20 present the exact two-sided 95% confidence interval (CI) for a sample size of 400 subjects, according to the value observed for the seroprotection status for diphtheria and tetanus, seropositivity for the pertussis antigens and booster response to all antigens.

In addition, Table 21 presents the exact two-sided 95% CI for a sample size of 100 subjects (per age category), according to the value observed for the seroprotection status for diphtheria and tetanus, seropositivity for the pertussis antigens and booster response to all antigens.

Table 18 Exact two-sided 95% CI for a sample size of 400 subjects according to the value observed for seroprotection status for diphtheria and tetanus

Observed rate expressed as a percentage (number of subjects reporting seroprotection for diphtheria and tetanus antigens)	Exact two-sided 95% CI for this observed rate for a sample size of 400 subjects	
	Lower Limit	Upper Limit
90(360)	86.6	92.8
91.1(364)	87.8	93.6
95(380)	92.4	96.9
96.2(385)	93.9	97.9
99.5(398)	98.2	99.9
100(400)	99.1	100

Reference data: Please refer Table 22.

Table 19 Exact two-sided 95% CI for a sample size of 400 subjects according to the seropositivity for the pertussis antigens

Observed rate expressed as a percentage (number of subjects reporting seropositivity for the pertussis antigens)	Exact two-sided 95% CI for this observed rate for a sample size of 400 subjects	
	Lower Limit	Upper Limit
90(360)	86.6	92.8
95(380)	92.4	96.9
98.6(394)	96.8	99.4
99.1(396)	97.5	99.7
99.5(398)	98.2	99.9
100(400)	99.1	100

Reference data: Please refer [Table 22](#).

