N = number of subjects included in the PP cohort for immunogenicity

D and T: % of subjects with antibody concentration ≥0.1 IU/ml; PT, FHA and PRN: % of subjects with antibody concentration ≥5 EL.U/ml.

VR= Vaccine response:

Booster responses to the diphtheria and tetanus antigens, defined as:

For subjects with pre-vaccination concentration below seroprotection cut-off (<0.1 IU/ml): antibody concentrations at least ≥0.4 IU/ml one month after vaccination.

For subjects with pre-vaccination concentration equal or above seroprotection cut-off (≥0.1 IU/ml): an increase in antibody concentrations of at least four times the pre-vaccination concentration one month after vaccination.

Booster response to the PT, FHA and PRN antigens, defined as:

For initially seronegative subjects (pre-vaccination concentration below cut-off: <5 EL.U/ml): antibody concentrations at least four times the cut-off (post-vaccination concentration ≥20 EL.U/ml)

For initially seropositive subjects with pre-vaccination concentration ≥5 EL.U/ml and <20 EL.U/ml: an increase in antibody concentrations of at least four times the pre-vaccination concentration.

For initially seropositive subjects with pre-vaccination concentration ≥20 EL.U/ml: an increase in antibody concentrations of at least two times the pre-vaccination concentration.

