10.5. Derived and transformed data

- A seronegative subject is a subject whose antibody concentration is below the assay cut-off value.
- A seropositive subject is a subject whose antibody concentration is greater than or equal to the assay cut-off value.
- A seroprotected subject is a subject whose antibody concentration is greater than or equal to the level defining clinical protection. The following seroprotection thresholds are applicable:
 - Anti-diphtheria antibody concentrations ≥ 0.1 IU/ml *for ELISA assay and ≥ 0.1 IU/ml for Vero-cell assay. (Amended 31 October 2017)*
 - Anti-tetanus antibody concentrations ≥ 0.1 IU/ml.
- Other cut-offs to be considered:
 - Anti-diphtheria antibody concentrations ≥ 1.0 IU/ml.
 - Anti-tetanus antibody concentrations ≥ 1.0 IU/ml.
- Booster response to Diphtheria and Tetanus antigens is defined as:
 - for subjects with pre-vaccination antibody concentration < 0.1 IU/ml (i.e. below the seroprotection cut-off), antibody concentrations at least ≥ 0.4 IU/ml, one month after vaccination, and
 - for subjects with pre-vaccination antibody concentration ≥ 0.1 IU/ml (i.e. equal or above the seroprotection cut-off), an increase in antibody concentrations of at least four times the pre-vaccination concentration, one month after vaccination.
- Booster response to PT, FHA and PRN antigens is defined as:
 - for subjects with pre-vaccination antibody concentration below the assay cut-off, post-vaccination antibody concentration \geq four times the assay cut-off,
 - for subjects with pre-vaccination antibody concentration between the assay cut-off and below four times the assay cut-off, post-vaccination antibody concentration \geq four times the pre-vaccination antibody concentration, and
 - for subjects with pre-vaccination antibody concentration \geq four times the assay cut-off, post-vaccination antibody concentration \geq two times the pre-vaccination antibody concentration.
- The geometric mean concentration (GMC) calculations are performed by taking the anti-log of the mean of the \log_{10} concentration transformations. Antibody concentrations below the cut-off of the assay will be given an arbitrary value of half the cut-off for the purpose of GMC calculation.

Handling of missing data:**Immunogenicity:**

- For a given subject and a given immunogenicity measurement, missing or non-evaluable measurements will not be replaced.

Reactogenicity and Safety:

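### Primary diphtheria seroprotection: Sections 5.7.5 and 10.5 give Vero-cell thresholds ten times apart, and the joint wording can work only as a sequential *or*

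*Protocol*

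**What the plan says.** Section 10.1 makes anti-diphtheria seroprotection one month after vaccination part of the primary endpoint. Its footnote sends sera below 0.1 IU/ml by ELISA to a Vero-cell neutralisation assay. Three places then bear on how a subject is scored.

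- Section 5.7.5, current text, on the primary endpoint: "Both the ELISA test (antibody concentrations ≥ 0.1 IU/ml) and Vero-cell test (antibody concentration ≥ 0.01 IU/ml) will define the seroprotection status". The same section gives the Vero-cell assay cut-off as 0.004 IU/ml, treats 0.01 IU/ml and above as protective, and defines a diphtheria non-responder as Vero-cell below 0.01 IU/ml.
- Section 10.5, current text, under the seroprotection thresholds: 0.1 IU/ml "for ELISA assay and ≥ 0.1 IU/ml for Vero-cell assay".
- Appendix B. Under Amendment 2 the rule was "The ELISA test will define the seroprotection status for the primary endpoint". The Amendment 3 entry for Section 5.7.5 reads "Both, the ELISA test (antibody concentrations ≥ 0.1 IU/ml) and Vero-cell test (antibody concentrations ≥ 0.01 IU/ml", and its entry for Section 10.5 gives "0.01 IU/ml for Vero-cell assay".

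Section 10.7 reports seroprotection rates before and one month after vaccination with exact 95% confidence intervals. Section 10.9 makes all analysis descriptive. In Section 10.3, Table 18 carries the note "Reference data: Please refer Table 22", and the notes to Table 22 define its rates as "D and T: % of subjects with antibody concentration ≥0.1 IU/ml".

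**The concern.** A primary binary endpoint needs one rule that places every serum in one class. Here there are two obstacles.

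First, Section 5.7.5 joins the two tests as if both had to be met, yet the testing scheme runs the second only on sera that have failed the first.

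Second, the section that turns concentrations into seroprotection status uses a Vero-cell threshold ten times the one in 5.7.5 (0.1 / 0.01 = 10). Both sections are current text and both are marked as amended on 31 October 2017, so date does not settle which governs.

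At stake is the reported primary diphtheria rate and its interval, overall and by age stratum. The pre-vaccination seroprotection rate in Section 10.7 uses the same rule and is affected in the same way.

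**Working it through.** **Inputs.** ELISA threshold 0.1 IU/ml (5.7.5 and 10.5). Vero-cell threshold 0.01 IU/ml (5.7.5) or 0.1 IU/ml (10.5). Vero-cell run only if ELISA is below 0.1 IU/ml (10.1, and the notes to Tables 8 and 9). Evaluable N = 400, or 100 per stratum (10.3). Diphtheria rates in Table 22: 100, 96.2, 91.1, 100, 99.5, 100, 99.3 and 100%.

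**The plan's own figures.** 100 / (1 − 0.10) = 111.1, rounded up to 112; 4 × 112 = 448, as stated. Clopper-Pearson limits reproduce Table 18: 364/400 gives 87.8 to 93.6 and 385/400 gives 93.9 to 97.9.

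**Classification of every possible serum (IU/ml).**

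| ELISA | Vero-cell | 5.7.5 read as *or* | 10.5 read as *or* | Either, read as *both* |
|---|---|---|---|---|
| ≥0.1 | not run | yes | yes | no (no second result) |
| <0.1 | ≥0.1 | yes | yes | no |
| <0.1 | 0.01 to <0.1 | **yes** | **no** | no |
| <0.1 | <0.01 | no | no | no |

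Read literally as *both*, no subject could be seroprotected, so that reading can be set aside. Read as *or*, the two sections differ in the third row only. A post-vaccination serum in that row is not seroprotected under 10.5, yet it is not a diphtheria non-responder under 5.7.5. The assay cut-off of 0.004 IU/ml lies below both thresholds, so the assay does not rule either one out.

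**Size of the disagreement.** Let E be the proportion at or above 0.1 IU/ml by ELISA. Among sera below it, let h be the share with Vero-cell ≥0.1 and g the share from 0.01 to <0.1.

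- Rate under 10.5 = E + h(1 − E)
- Rate under 5.7.5 = E + (h + g)(1 − E)
- Difference = g(1 − E), which cannot exceed 1 − E

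The protocol gives neither g nor h. The table sets h = 0, so the 10.5 rate equals E, and varies g. E is taken from Table 18 rows that match Table 22 diphtheria rates, on the assumption that those are ELISA rates (Table 22 names no assay).

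| E (10.5 rate, 95% CI) | g | 5.7.5 rate (95% CI) | Difference, points |
|---|---|---|---|
| 364/400 = 91.0% (87.8–93.6) | 0 | 91.0% (87.8–93.6) | 0 |
| same | 0.25 | 373/400 = 93.3% (90.3–95.5) | 9/400 = 2.25 |
| same | 0.5 | 382/400 = 95.5% (93.0–97.3) | 18/400 = 4.5 |
| same | 1 | 400/400 = 100% (99.1–100) | 36/400 = 9.0 |
| 385/400 = 96.25% (93.9–97.9) | 0.5 | 392/400 = 98.0% (96.1–99.1) | 7/400 = 1.75 |
| same | 1 | 400/400 = 100% (99.1–100) | 15/400 = 3.75 |

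The other six Table 22 values run from 99.3 to 100%, where the difference is at most 100 − 99.3 = 0.7 points.

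**The case against.** The best defence is that nobody would be misled. Section 5.7.5 names 0.01 IU/ml explicitly for the primary endpoint, its non-responder definition uses the same value, and so does the amendment log for Section 10.5. The threshold in 10.5 therefore looks like a copying slip. The sequential *or* follows from the testing scheme, which the protocol repeats several times. An unseen SAP may already state one clean rule.

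Much of that stands. The *both* wording is a drafting fault that a careful reader can resolve, and the log points towards 0.01 IU/ml. A difference between a log and current text would not be a finding by itself. What remains is a conflict between two current sections on the primary endpoint, one of them the section a programmer would use to derive it. A SAP could choose one value, but the protocol would still contradict itself.

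A reader might go further and infer that adding the Vero-cell route lets the primary rate exceed its own reference in Table 22 by definition alone, and that leaving out an ELISA-only rate is an error. The route is indeed absent from Table 22's stated definition, and a second chance for ELISA failures cannot lower the rate. But nothing is tested against Table 22. Analysis is descriptive, the sample size rests on a regulatory minimum of 100 per age group, and the reference rates only supply illustrative rows for the interval tables. Their definition is printed under Table 22. An ELISA-only tabulation is the kind of detail a SAP may carry. The mismatch touches informal interpretation only.

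**Conclusion.** The primary diphtheria rule is stated inconsistently and needs correction. The reported rate depends on whether the analyst follows 5.7.5 or 10.5, and the gap is exactly the share of sera with ELISA below 0.1 and Vero-cell from 0.01 to below 0.1 IU/ml.

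That share is unknown. The 9.0-point figure is a ceiling, not an expectation: it applies the lowest of eight reference rates, from a cohort aged 40 and over, to all 400 subjects and assumes that every ELISA failure falls in the disputed band. If few post-vaccination sera fall below 0.1 IU/ml by ELISA, the practical effect is close to nil. No test, margin, success rule or sample size is affected. The finding is minor in cost but concerns the definition of a primary endpoint.

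**What to change.** Reconcile Section 10.5 with Section 5.7.5 and put the same sentence in both: a subject is seroprotected against diphtheria if ELISA is at or above 0.1 IU/ml or, when ELISA is below 0.1 IU/ml, if Vero-cell is at or above the single reconciled threshold. That threshold is 0.01 IU/ml according to 5.7.5 and the Amendment 3 log; the sponsor should confirm it and check that the analysis code uses it at both timepoints.

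Optional, and not the correction of an error: show the ELISA-only rate at 0.1 IU/ml with its exact interval beside the combined rate, so that the Vero-cell contribution is visible. Table 8 describes that assay as still being re-developed. The row should not be labelled comparable with Table 22, because the assay behind those rates is not named and this trial's ELISAs were re-developed.

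The cost is a wording change in two sections and, if wanted, one table row from data already collected. The 448 enrolled, the combined endpoint and the exact intervals stay as they are.
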